1.2.2. Secondary Endpoints

- a. Determine the rates of complete pathologic remission and downstaging achieved with the investigational treatment at the time of surgery.
- b. Determine the changes in tumor cell proliferation by means of changes in Ki67 expression and changes in serum concentration of markers of angiogenesis (VEGF-A, soluble VEGFR2, activin A and activin B, angiopoietin-1 and -2, TGF- β , soluble endoglin) before and after the investigational treatment and correlate with clinical, radiographic, and pathologic response.

c. Determine the C_{max} , T_{max} , AUC, $T_{1/2}$, clearance of everolimus and TRC105 when used in combination with letrozole.

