5.4.2 Treatment Phase

The following evaluations and procedures will be performed during the **treatment phase**: (All assessments should be performed within 5 working days of the protocol-specified date).

- Physical examination, vital signs, weight, and performance status on weeks 4, 8, 12, 16, 20 and 24.
- Laboratory assessments: CBC with differential and platelet count, serum chemistries (glucose, BUN, creatinine, total protein, albumin, bilirubin, calcium, alkaline phosphatase, AST, and ALT), and serum electrolytes (Na, K, Cl) on week 1 and at the beginning of each cycle until week 24.
- Lipid panel (cholesterol, triglycerides, HDL, and LDL) in a fasting state (at least 8 hours) should be obtained at least on cycle 2 and, if elevated, repeated on each cycle until recovery to baseline value or grade 1 (see 5.2.2.2 for management of hyperlipidemia and hyperglycemia).

Serum estradiol levels on weeks 4, 12, and 20 in women receiving goserelin.

- Hepatitis panel as clinically indicated.
- Research biopsy (core needle biopsy of the tumor) at week 4 (required).
- Tumor assessments: Ultrasound of the breast will be obtained on week 4, 8, 12, 16, 20 and 24. Mammogram will be obtained on week 24. Additional PET scans or CT of the chest, abdomen, and pelvis, or bone scans are not required during treatment phase except as clinically indicated (see section **7.2 Measurement of Effect**). MRI breast will be obtained at baseline, week 12 and 24.
- Evaluation of the ejection fraction with an echocardiogram/MUGA only as clinically indicated.
- Surgical evaluation at the end of neoadjuvant therapy. **There must be at least 4 weeks between the last dose of everolimus and TRC105 and surgery.** Patients will continue letrozole until the day before surgery.
- Concomitant medication assessment.
- Assessment of adverse events.

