5.4.3 Safety Follow-up Phase

Patients will complete participation in the protocol at the time of surgery and will not be followed unless the patient requires follow up of adverse events. The following evaluations and procedures will be performed at **early termination**. Every effort should be undertaken for the following procedures to be completed within 10 days.

- Clinical evaluations: Weight, physical examination (complete), vital signs and performance status. There must be a complete and clear documentation of objective response or disease progression using the RECIST criteria. Reason(s) for discontinuation must be documented.
- Laboratory assessment: UA, CBC with differential and platelet count, serum chemistries (glucose, BUN, creatinine, total protein, albumin, bilirubin, calcium, alkaline phosphatase, AST, and ALT), serum electrolytes (Na, K, Cl), and lipid panel (cholesterol, triglycerides, HDL, and LDL) in a fasting state (at least 8 hours).
- Tumor assessments: Mammogram, breast ultrasound, and breast MRI. Spiral CT scans of chest, abdomen, and pelvis, bone scan, and any other procedure are not required per protocol but will be obtained if clinically indicated.
- Concomitant medication assessment.
- Assessment of adverse events. If the patient has an ongoing toxicity, the patient should be followed until resolution or stabilization. Serious and non-serious adverse events occurring

within 30 days of day 0 of the last treatment should be reported on the appropriate adverse event CRF.

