10. STATISTICAL CONSIDERATIONS

This is a phase I/II study with the primary objective to characterize the tolerability and feasibility of a novel combination of agents. The Primary Endpoint is defined as the determination of MTD and RP2D and rates of treatment-related toxicities. The secondary efficacy endpoints are rates of pCR or down-staging. The principal investigator will hold the IND for the trial (Appendix F).

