10.2 Statistical Analysis

The primary analysis is of safety and will include any patients who receive at least one dose of the investigational regimen. The rate of adverse events will be estimated at the end of the study along with two-sided 95% exact CIs (Clopper-Pearson intervals). At the completion of the study, the secondary endpoint of pCR or downstaging rate will be estimated along with two-sided 95% CIs with the exact method of Clopper-Pearson intervals. Secondary endpoint analysis will be descriptive. Mean, median, geometric mean, range and coefficient of variation will be used to describe continuous demographic variables. Frequency and proportion will be used to describe categorical variables.

We will use descriptive statistics (mean, median, geometric mean, coefficient of variation, and 95% confidence intervals) and graphical displays (mean concentration-time graphs, scatter plots, box plots or spaghetti plots) to evaluate the pharmacokinetic parameters of the TRC105 and everolimus. We will use descriptive statistics (mean, median, geometric mean, coefficient of variation, and 95% confidence intervals) and graphical displays (scatter plots, box plots, plots of PD parameters against PK data) to analyze the changes in markers of proliferation and angiogenesis with the investigational treatment.

Exploratory analysis will be conducted on the correlations between clinical outcomes and pharmacodynamic biomarkers or translation profiles. Translational profiles will be analyzed between responders and non-responders and the differences between responders and non-responders will be presented in scatter plots along with corresponding 95% CI. Quartile normalization and logarithmic transformation will be conducted before analysis. Logistic regression analysis will be used to predict response with translational profiles or biomarkers with or without adjustment for covariates, e.g. age. Multivariate Cox proportional hazards model will be used to identify a set of biomarkers for prediction of response. Odds ratios with 95% CIs will be calculated for each significant biomarker in terms of predicting response. However, it is recognized that sample size may be too small for such analyses and these analyses are conducted only to generate hypotheses that will require further validation.

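### Section 10.2 names a Cox model to select biomarkers for a yes/no response, with no time scale defined, and then promises odds ratios that belong to logistic regression

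*Combined protocol and SAP*

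**What the plan says.** The last paragraph of Section 10.2 describes the exploratory biomarker analyses in four steps:

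- The comparison is between two groups: "Translational profiles will be analyzed between responders and non-responders".
- A binary-outcome model comes first: "Logistic regression analysis will be used to predict response with translational profiles or biomarkers". Covariates are optional, and age is the example given.
- A second model is then named for choosing markers: "Multivariate Cox proportional hazards model will be used to identify a set of biomarkers for prediction of response".
- The effect measure promised is the odds ratio: "Odds ratios with 95% CIs will be calculated for each significant biomarker in terms of predicting response".

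It closes by conceding that the sample may be too small and that the results only generate hypotheses for later validation.

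Elsewhere, Section 10 states that "The secondary efficacy endpoints are rates of pCR or down-staging", and Section 1.2.2(a) reads "Determine the rates of complete pathologic remission and downstaging achieved with the investigational treatment at the time of surgery". Section 1.2.2(b) also wants markers correlated with clinical and radiographic response. Section 7.2.4 defines clinical, radiographic and pathologic response and says all three will be reported. Section 7.3.3 plans to correlate biopsy data with complete and objective response. The only time quantities are in Section 7.2.7: duration of response, of clinical complete response and of stable disease.

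**The concern.** A Cox model needs a time for each patient: a start, an event date for responders and a censoring date for the others. Section 10.2 supplies none, and the paragraph otherwise treats response as binary. The odds ratio in the next sentence is the natural output of the logistic model already planned, not of a proportional hazards fit. An analyst following the text would have to invent a time scale and a tie rule, or quietly replace the model.

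At stake are the set of markers carried forward and their reported effect sizes. Both could depend on unstated choices. The commitment to odds ratios for significant markers adds a smaller problem. No threshold is given, and the text does not say whether the other markers' estimates will appear.

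**Working it through.** **1. Is a time to response defined anywhere?**

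- Sections 1.2.2(a) and 10: rates of pCR and downstaging, determined at surgery. These are proportions with one reading per patient.
- Section 7.2.7: the duration-of-response clock starts when response criteria are met, so it does not measure time to response. The stable-disease clock starts with treatment but does not end at response.
- Section 5.4.3: "Patients will complete participation in the protocol at the time of surgery and will not be followed" unless adverse events require it. There is no later period in which a pathologic response could be timed.
- Section 5.4.2: "There must be at least 4 weeks between the last dose of everolimus and TRC105 and surgery". This sets a minimum interval only. Time to a pathologic response would be time to the operation.
- Sections 5.4.2 and 7.2.4: ultrasound at weeks 4 to 24 and caliper measurement at each visit. A time to clinical or radiographic response could be built from these, but no origin, event date, censoring or tie rule is written down.

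**2. How many responders?** The plan gives no figure for the biomarker analysis. The exact intervals in Section 10.1 fix the responder counts it has in mind. For 2/20, 4/20 and 6/20 the Clopper-Pearson limits are 1.23–31.70%, 5.73–43.66% and 11.89–54.28%. These match the stated 1.2–31.7%, 5.7–43.6% and 11.8–54.3%, apart from truncation of two limits. So the plan's 10%, 20% and 30% scenarios mean 2, 4 or 6 responders among 20. At the 45% downstaging that Section 2.1.5 reports for letrozole with bevacizumab, the count would be 0.45 × 20 = 9. Section 7.3.4 expects only about 8 surgical specimens for ribosomal profiling.

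**3. Does the model matter for a response read once?** Inputs (invented): 10 marker-high and 10 marker-low patients, all placed at one common time, none censored earlier. All p-values are from likelihood-ratio tests.

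For 7/10 versus 2/10 (9 of 20 respond):

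- Logistic: OR = (7 × 8)/(3 × 2) = 9.33. LR = 2[7 ln 0.7 + 3 ln 0.3 + 2 ln 0.2 + 8 ln 0.8 − 9 ln 0.45 − 11 ln 0.55] = 2[−11.113 + 13.763] = 5.30, p = 0.021.
- Cox, Breslow ties: HR = (7/10)/(2/10) = 3.50. LR = 2[7 ln(7/4.5) + 2 ln(2/4.5)] = 2.94, p = 0.086.
- Cox, Efron ties: maximising the partial likelihood numerically gives HR 4.92, LR 4.83, p = 0.028.

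Other splits:

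| Responders, high vs low | Logistic OR (p) | Breslow HR (p) | Efron HR (p) |
|---|---|---|---|
| 7/10 vs 2/10 | 9.33 (0.021) | 3.50 (0.086) | 4.92 (0.028) |
| 7/10 vs 1/10 | 21.0 (0.004) | 7.00 (0.024) | 10.4 (0.006) |
| 6/10 vs 2/10 | 6.00 (0.063) | 3.00 (0.148) | 3.84 (0.075) |
| 3/10 vs 1/10 | 3.86 (0.25) | 3.00 (0.31) | 3.27 (0.27) |

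The effect measure differs in every row. The verdict at 5% differs only in the first. Fisher's exact test for that row gives p = 0.070, so the ordinary logistic p-value is itself fragile at this size.

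**4. If a clinical response clock were used instead.** For invented data of 4/10 versus 1/10, logistic regression gives OR = (4 × 9)/(6 × 1) = 6.00 (95% CI 0.53–67.6). Responders were given random 4-weekly response times and non-responders were censored at week 24. The Breslow HR then runs from about 4.0 to 5.0 (2.5th to 97.5th percentile). This is a modest spread, but still a different quantity from the odds ratio.

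**The case against.** The strongest reply is that this is a drafting slip in an analysis the plan itself plays down. The odds-ratio sentence suggests that multivariable logistic regression was meant, and no dose, stopping, safety or efficacy result depends on it. That stands as a limit on importance. It does not remove the defect: the caveat concerns sample size, and no sample size supplies a missing time scale.

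A technical reply is that a discrete-time treatment of ties, with everyone at one time, would produce a conditional odds ratio. That would be conditional logistic regression under another name, and the plan does not specify it.

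A reader might infer that response is seen only at surgery, so that any Cox analysis is impossible. The documents do not support this. Sections 1.2.2(b), 5.4.2, 7.2.4 and 7.3.3 plan repeated clinical and imaging assessment and correlations with those responses, so a time to response could be defined. It simply has not been. For the same reason, the common-time figures apply to pCR or downstaging, not to every response type.

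A reader might also take 7/10 versus 2/10 as typical. It lies close to a 5% threshold that is assumed, and its 9 responders exceed the 2 to 6 in Section 10.1.

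Finally, the plan does not say that non-significant odds ratios will be withheld. The threshold issue is missing detail about reporting, not a demonstrated bias.

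**Conclusion.** The point holds in a limited form. As written, the Cox estimate is undefined and its stated effect measure does not match the model. For pCR or downstaging it is the wrong model; for clinical or radiographic response it could be made valid only by adding definitions that are absent.

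On tied, common-time data the choice always changes the effect measure and can change the p-value across 5% (0.021, 0.086 or 0.028 in one invented table), though it did not in the other three tables. These figures rest on assumed marker splits, an assumed 5% level and no early censoring.

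A reader might infer that the trial's efficacy or safety conclusions are at risk. They are not: MTD/RP2D, the adverse-event rates, the Gehan rule and the pCR/downstaging estimate with its exact interval do not use this model. The change is worth making because the text is wrong as it stands and the correction is nearly free.

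**What to change.** In Section 10.2:

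1. Replace the Cox sentence with multivariable logistic regression, fitted separately for each binary response definition: pCR or downstaging at surgery, and the clinical and radiographic/objective responses already planned in Sections 1.2.2(b), 7.2.4 and 7.3.3. State each definition, so that no planned correlation is lost.
2. Specify a penalised or exact fit with very few covariates per model, because 2 to 6 responders among 20 cannot support more.
3. Keep a Cox model only if time to clinical or radiographic response is explicitly defined (origin, event date, censoring, tie handling), and then report hazard ratios.
4. List the markers in advance and report the odds ratio with 95% CI for every one, whatever its p-value. With full reporting, no significance threshold is needed.

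The cost is a few sentences in the statistical section, with no new patients, samples or assessments.

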10.3 Stratification Factors

No *a priori* stratification of patients will be undertaken in this study. Subgroup analyses will be conducted *a posteriori* according to grade (grade II vs. III), stage (stage IIA and IIB vs. IIIA and IIIB) lymph node involvement (N0 vs. N1-2), age (as a continuous variable). It is recognized that sample size may be too small for such analyses and these analyses are exploratory to generate hypotheses and will require further validation.

11. PROTOCOL ADHERENCE

Investigators ascertain they will apply due diligence to avoid protocol deviations. No authorized deviations are permitted. If an investigator feels a protocol deviation would improve the conduct of the study this must be considered a protocol amendment, and unless such an amendment is agreed upon by the principal investigator and approved by the IRB it cannot be implemented. All significant protocol deviations will be recorded and reported in the CSR.

APPENDIX A

Performance Status Criteria

ECOG Performance Status Scale		Karnofsky Performance Scale	
Grade	Descriptions	Percent	Description
0	Normal activity. Fully active, able to carry on all pre-disease performance without restriction.	100	Normal, no complaints, no evidence of disease.
		90	Able to carry on normal activity; minor signs or symptoms of disease.
1	Symptoms, but ambulatory. Restricted in physically strenuous activity, but ambulatory and able to carry out work of a light or sedentary nature (e.g., light housework, office work).	80	Normal activity with effort; some signs or symptoms of disease.
		70	Cares for self, unable to carry on normal activity or to do active work.
2	In bed <50% of the time. Ambulatory and capable of all self-care, but unable to carry out any work activities. Up and about more than 50% of waking hours.	60	Requires occasional assistance, but is able to care for most of his/her needs.
		50	Requires considerable assistance and frequent medical care.
3	In bed >50% of the time. Capable of only limited self-care, confined to bed or chair more than 50% of waking hours.	40	Disabled, requires special care and assistance.
		30	Severely disabled, hospitalization indicated. Death not imminent.
4	100% bedridden. Completely disabled. Cannot carry on any self-care. Totally confined to bed or chair.	20	Very sick, hospitalization indicated. Death not imminent.
		10	Moribund, fatal processes progressing rapidly.
5	Dead.	0	Dead.

APPENDIX B
Drugs with potential interactions with everolimus

CYP3A4 inhibitors		CYP3A4 inducers	
Alosetron	Aprepitant	Alosetron	Aprepitant
Atorvastatin	boceprevir	Bexarotene	uprenorphine
Bosentan	buprenorphine	Buspiron	cyclosporine
Buspirone	carbamazepine		diltiazem
clarithromycin	conivaptan		docetaxel
Coumadin	cyclosporine		efavirenze
Diazepam	Valdecoxib		erlotinib
dihydroergotamine mesylate			estazolam
diltiazem	docetaxel		exemestane
dofetilide	efavirenz		fosamprenavir
eplerenone	estazolam		galantamine
fentanyl	fosamprenavir		gefitinib
galantamine	gefitinib		imatinib
grapefruit juice	imatinib		irinotecan
indinavir	itraconazole		itraconazole
ketoconazole			lopinavir/ritonavir
lopinavir/ritonavir			methadone
lovastatin	methadone		mifepristone
mibefradil,	mifepristone		modafinil
nefazodone,	nelfinavir		nisoldipine
paclitaxel	pimozide		paclitaxel
propafenone	posaconazole		pimozide
quinidine	ranolazine		quinidine
rifampin	rifabutin		sirolimus
ritonavir	saquinavir		solifenacin succinate
simvastatin	sirolimus		sunitinib
solifenacin	succinate		tacrolimus
tacrolimus	telaprevir,		tramadol
telithromycin	tinidazole		tinidazole
valdecoxib	valdenafil		valdecoxib
vinorelbine			voriconazole
voriconazole			zonisamide
zonisamide			

APPENDIX C

American College of Radiology (ACR) Practice Guidelines for Imaging Studies of the Breast

The ACR Practice Guideline for the Performance of Screening and Diagnostic Mammography,
<http://www.acr.org/~media/3484ca30845348359bad4684779d492d.pdf>

The ACR Practice Guideline for the Performance of a Breast Ultrasound Examination,
<http://www.acr.org/~media/52D58307E93E45898B09D4C4D407DD76.pdf>

The ACR Practice Guideline for the Performance of Contrast-Enhanced MRI of the Breast,
<http://www.acr.org/~media/2A0EB28EB59041E2825179AFB72EF624.pdf>

APPENDIX D

NCI Common Terminology Criteria for Adverse Events (NCI CTCAE) version 4.03
http://evs.nci.nih.gov/ftp1/CTCAE/CTCAE_4.03_2010-06-14_QuickReference_8.5x11.pdf

APPENDIX E

FDA MedWatch 3500A Form

<http://www.accessdata.fda.gov/scripts/MedWatch>

APPENDIX G

Blood and Biopsy Procedures

UAB 1514 - Blood Draw and Biopsy Schedule

Paraffin blocks to UAB
Frozen biopsies to UAB
Blood for Serum Collection (PK, PD, APA)

A. UAB - Paraffin blocks (all patients)

Pre-therapy paraffin blocks and core research biopsies (all patients) will be obtained and prepared. Time points include baseline, cycle 2 day 1 and at the time of surgery. Formalin-fixed paraffin embedded tissue blocks from the patient's primary tumor collected for diagnostic purposes will be requested for all patients enrolled in the study at the time of registration. For the research cores, the goal is for 2-4 core biopsy specimens obtained using standard institutional guidelines for a diagnostic core biopsy of a breast mass. However, biopsy samples will preferably be obtained using a 14-18 gauge core needle. At least one core will be used to prepare a paraffin block (paraffin-embedded blocks or formalin fixed tissue) and at least one core will be immediately frozen (snap frozen individually for gene expression).

Snap frozen research biopsies will be sent to UAB Tissue Procurement where biopsies will be stored for batching. The batched biopsies will then be forwarded to HudsonAlpha Institute for Biotechnology. These biopsies should be labeled with an indelible marker to include:

1. The clinical trial identification number (UAB 1514)
2. The subject's study number
3. The date of acquisition

Fifteen slides will be prepared from the paraffin blocks or formalin fixed tissue by [name] at UAB for analysis by conventional IHC of ER, PR, Her-2, EGFR, Ki67, apoptotic markers, and biomarkers of DNA repair such as H2AX and BRCA localization.

B. UAB – Snap-Frozen research biopsies (all patients)

All cryovials (NALGENE® Cryoware™ 5000-0000) will be labeled with an indelible marker to include:

1. The study identification number (UAB 1514);
2. The subject's study number;
3. The date of acquisition

[name]'s Lab
Lab Contact: [name]
University of Alabama at Birmingham
CCC PK/PD Core Laboratory
[name]

Preparing Tissue in Frozen Cryovials

Snap Freezing: Do not Cut the tissue and simply ship as is. Place each core of tissue into a labeled individual 2.0 ml NALGENE® Cryoware™ cryovials. The label should contain the UAB clinical trial number (UAB 1514) followed by the subject's study number, as well as the date the specimen was collected. Do not place the patient's name or medical record number on the label. The container will become very cold. Do not handle with unprotected hands. Safety goggles should be use throughout the procedure. Snap freeze samples in liquid nitrogen. If not available, you may use an alcohol/dry ice bath. Fill pan about 1-2 inches deep with methanol. The depth should be enough to cover the height of the vial. Slowly add crushed dry ice until the boiling stops. The bath is now ready for use. Drop the sealed vials directly into the liquid nitrogen (LN₂) carefully. Leave the vials in the liquid nitrogen for at least one minute. Once frozen, transfer the samples using tongs or a large spoon to remove the vials from the liquid nitrogen and transfer to a -80 °C freezer until shipped.

C. Serum (PK, PD, APA)

1. Blood samples for the assays will be taken at the times described in the protocol. Serum will be obtained in red top serum separator tubes and will be sent to [name]'s Lab. **[name] lab should be notified of these samples. The laboratory address is:**

[name]'s Lab
Lab Contact: [name]
University of Alabama at Birmingham
CCC PK/PD Core Laboratory
[name]

2. **PK: A 5 mL blood sample will be collected pre-dose and 1, 2, 4, 6 and 24 hours post-dose on the days indicated within Table 7-1: Study Calendar. Samples will be separated and stored at approximately -70 °C.**

[name]'s Lab
Lab Contact: [name]
University of Alabama at Birmingham
CCC PK/PD Core Laboratory
[name]

APA: Anti-Product Antibody (APA) will be collected will be collected before dosing on cycle 1 day 1, every 4 weeks thereafter, 4 and 12 weeks following the last dose of TRC105

(Table 7-1: Study Calendar). Concentrations will be measured using validated ELISA methods. APA concentrations will be evaluated in the context of pharmacokinetic parameters and AE profiles. Samples will be separated and stored at approximately -70 °C.

[name]'s Lab

Lab Contact: [name]

University of Alabama at Birmingham

CCC PK/PD Core Laboratory

[name]
